### Reporting of Serious Adverse Event

Serious Adverse Event Reporting via Paper Case Report Form (SAER Form)

• Facsimile transmission of the Serious Adverse Event Report Form (see Figure 2) is the preferred method to transmit this information.

• In rare circumstances and in the absence of facsimile equipment, notification by telephone is acceptable with a copy of the Serious Adverse Event Report Form sent by overnight mail or courier service.

• Initial notification via telephone does not replace the need for the Investigator to complete and sign the Serious Adverse Event Report Form within the designated reporting time frames.

Approved

**Figure 2: Sample Serious Adverse Event Report Form**

AMGEN*** 20090231 Covance Study#: 8405952 omecamtiv mecarbil (AMG 423)	Clinical Trial Serious Adverse Event Report - Phase 1- 4 Notify Amgen (Sponsor) Within 24 Hours of knowledge of the event						 New  Follow-up																																																								
Amgen (Sponsor) UK Safety [contact]																																																															
1. SITE INFORMATION 
 
 Site Number	Investigator	Country	Date of Report	
 
  	 	 	 	 	 	Day	Month	Year	
 
 Reporter	Phone Number	( )	
 
 		( )	
 
								Site Number	Investigator			Country		Date of Report									Day	Month	Year	Reporter				Phone Number		( )									( )																						
Site Number	Investigator			Country		Date of Report																																																									
						Day	Month	Year																																																							
Reporter				Phone Number		( )																																																									
						( )																																																									
2. SUBJECT INFORMATION 
 
 Subject ID Number	Age at Event Onset	Sex	Race	If applicable, provide End of Study date	
 
  	 	□ F □ M	 	 	
 
								Subject ID Number	Age at Event Onset	Sex	Race	If applicable, provide End of Study date						□ F □ M																																													
Subject ID Number	Age at Event Onset	Sex	Race	If applicable, provide End of Study date																																																											
		□ F □ M																																																													
3. SERIOUS ADVERSE EVENT - Information in this section must also be entered on the Serious Adverse Event Summary CRF																																																															

Provide the date the Investigator became aware of this Serious Adverse Event Information: Day _____ Month _____ Year _____
 
 
  
Serious Adverse Event Diagnosis or Syndrome If diagnosis is unknown, enter Signs / Symptoms When Final Diagnosis is known, enter as Adverse Event  List one event per line. If event is fatal, enter the Cause of Death. Entry of "Death" is not acceptable, as this is an outcome.
 	Date Started	SAE Onset Time (24 hr clock)	Date Ended	SAE Stop Time (24 hr clock)	Check only if event occurred before first dose of IP (see codes below)	Enter Serious Criteria code	Relationship Is there a reasonable possibility that the event may have been caused by Amgen IP: omeamtiv mecarbil (AMG 423) If yes see section 10	Outcome of Event	Check only if event is related to study procedure eg. biopsy	
 
 Day Month Year	Day Month Year	 	 	 	 	 	 	01 Resolved 02 Resolving 03 Not Resolved 04 Fatal	 	
 
  	No ✓ Yes ✓	 	
 
  	
 
  	
 
 Serious Criteria: 01 Fatal 02 Immediately life-threatening	03 Required hospitalization 04 Prolonged hospitalization	05 Persistent or significant disability / incapacity 06 Congenital anomaly / birth defect	07 Other medically important serious event	 	
 
								
Serious Adverse Event Diagnosis or Syndrome If diagnosis is unknown, enter Signs / Symptoms When Final Diagnosis is known, enter as Adverse Event  List one event per line. If event is fatal, enter the Cause of Death. Entry of "Death" is not acceptable, as this is an outcome.
	Date Started	SAE Onset Time (24 hr clock)	Date Ended	SAE Stop Time (24 hr clock)	Check only if event occurred before first dose of IP (see codes below)	Enter Serious Criteria code	Relationship Is there a reasonable possibility that the event may have been caused by Amgen IP: omeamtiv mecarbil (AMG 423) If yes see section 10	Outcome of Event	Check only if event is related to study procedure eg. biopsy	Day Month Year	Day Month Year							01 Resolved 02 Resolving 03 Not Resolved 04 Fatal									No ✓ Yes ✓																				Serious Criteria: 01 Fatal 02 Immediately life-threatening		03 Required hospitalization 04 Prolonged hospitalization		05 Persistent or significant disability / incapacity 06 Congenital anomaly / birth defect		07 Other medically important serious event		

Serious Adverse Event Diagnosis or Syndrome If diagnosis is unknown, enter Signs / Symptoms When Final Diagnosis is known, enter as Adverse Event  List one event per line. If event is fatal, enter the Cause of Death. Entry of "Death" is not acceptable, as this is an outcome.
	Date Started	SAE Onset Time (24 hr clock)	Date Ended	SAE Stop Time (24 hr clock)	Check only if event occurred before first dose of IP (see codes below)	Enter Serious Criteria code	Relationship Is there a reasonable possibility that the event may have been caused by Amgen IP: omeamtiv mecarbil (AMG 423) If yes see section 10	Outcome of Event	Check only if event is related to study procedure eg. biopsy																																																						
Day Month Year	Day Month Year							01 Resolved 02 Resolving 03 Not Resolved 04 Fatal																																																							
							No ✓ Yes ✓																																																								
Serious Criteria: 01 Fatal 02 Immediately life-threatening		03 Required hospitalization 04 Prolonged hospitalization		05 Persistent or significant disability / incapacity 06 Congenital anomaly / birth defect		07 Other medically important serious event																																																									
4. HOSPITALIZATION 
 
 	Date and Time Admitted	Date and Time Discharged	
 
 	Day Month Year	Time (24H)	Day Month Year	Time (24H)	
 
  
Was subject hospitalized or was hospitalization prolonged due to this event? □ No □ Yes, If yes, please complete date(s) and time(s):
 	 	 	 	 	
 
												Date and Time Admitted		Date and Time Discharged						Day Month Year	Time (24H)	Day Month Year	Time (24H)	
Was subject hospitalized or was hospitalization prolonged due to this event? □ No □ Yes, If yes, please complete date(s) and time(s):
																																							
				Date and Time Admitted		Date and Time Discharged																																																									
				Day Month Year	Time (24H)	Day Month Year	Time (24H)																																																								

Was subject hospitalized or was hospitalization prolonged due to this event? □ No □ Yes, If yes, please complete date(s) and time(s):
																																																															
5. INVESTIGATIONAL PRODUCT (IP) 
Provide dosing details including date and time of the first dose and the dose just prior to or at event onset, and action taken (for the latest dose).
 
 
  omecamtiv mecarbil (AMG 423)   Open Label - (Part A)   ✓   Blinded – (Part B)   ✓ 	 Oral  Solution  Dosing 	Date and Time of First Dose	Date and Time of Latest Dose Prior to, or at time of Event and Action Taken with Product	
 
 Day / Month / Year	Time (24H)	Day / Month / Year	Time (24H)	Action Taken	Dose	Frequency	Lot # & Serial #	
 
 	 	 	 	 	 	 	Lot # _____ □ Unknown Serial # _____ □ Unknown	
 
 Action Taken with Product Codes:	01 Still being administered	02 Permanently discontinued	03 Withheld	 	
 
								omecamtiv mecarbil (AMG 423)  Open Label - (Part A)  ✓  Blinded – (Part B)  ✓	Oral Solution Dosing	Date and Time of First Dose		Date and Time of Latest Dose Prior to, or at time of Event and Action Taken with Product				Day / Month / Year	Time (24H)	Day / Month / Year	Time (24H)	Action Taken	Dose	Frequency	Lot # & Serial #									Lot # _____ □ Unknown Serial # _____ □ Unknown	Action Taken with Product Codes:		01 Still being administered		02 Permanently discontinued		03 Withheld																								
omecamtiv mecarbil (AMG 423)  Open Label - (Part A)  ✓  Blinded – (Part B)  ✓	Oral Solution Dosing	Date and Time of First Dose		Date and Time of Latest Dose Prior to, or at time of Event and Action Taken with Product																																																											
		Day / Month / Year	Time (24H)	Day / Month / Year	Time (24H)	Action Taken	Dose	Frequency	Lot # & Serial #																																																						
								Lot # _____ □ Unknown Serial # _____ □ Unknown																																																							
Action Taken with Product Codes:		01 Still being administered		02 Permanently discontinued		03 Withheld																																																									

Approved

AMGEN... 20090231  Covance Study#: 8405952 omecamtiv mecarbil (AMG 423)	Clinical Trial Serious Adverse Event Report - Phase 1-4 Notify Amgen (Sponsor) Within 24 Hours of knowledge of the event	 New  Follow-up
---	---	--

	Site Number		Subject ID Number										
6. CONCOMITANT MEDICATIONS (eg, chemotherapy)			Any Concomitant Medications?  No  Yes, If yes, please complete:										
Medication Name(s)	Start Date			Stop Date			Co-suspect No✓ Yes✓	Continuing No✓ Yes✓		Dose	Route	Freq.	Treatment M No✓ Yes✓
	Day	Month	Year	Day	Month	Year		No✓	Yes✓				
7. RELEVANT MEDICAL HISTORY (include dates, allergies and any relevant prior therapy)													

 
 
 
 
 
													

## Approved

AMGEN*** 20090231 Covance Study#: 8405952 omecamtiv mecarbil (AMG 423)	Clinical Trial Serious Adverse Event Report - Phase 1- 4 Notify Amgen (Sponsor) Within 24 Hours of knowledge of the event	 New  Follow-up
--	--	--

	Site Number	Subject ID Number	
10. CASE DESCRIPTION (Provide narrative details of events listed in section 3) - For each event in section 3, where relationship=Yes, please provide rationale.			
Signature of Investigator or Designee		Title	Date
I confirm by signing this report that the information on this form, including seriousness and causality assessments, is being provided to Amgen by the Investigator for this study, or by a Qualified Medical Person authorized by the Investigator for this study.			

Approved

## Appendix 2: Sample Storage and Destruction

Any blood sample collected according to the Schedule of Assessments ([Appendix 6](#)) can be analyzed for any of the tests outlined in the protocol and for any tests necessary to minimize risks to study subjects. This includes testing to ensure analytical methods produce reliable and valid data throughout the course of the study. This can also include, but is not limited to, investigation of unexpected results, incurred sample reanalysis, and analyses for method transfer and comparability.

All samples and associated results will be coded before being shipped from the site for analysis or storage. Samples will be tracked using a unique identifier that is assigned to the samples for the study. Results are stored in a secure database to ensure confidentiality.

Since the evaluations are not expected to benefit the subject directly or to alter the treatment course, the results of any exploratory studies are not placed in the subject's medical record and are not to be made available to the subject, members of the family, the personal physician, or other third parties, except as specified in the informed consent.

The subject retains the right to request that the sample material be destroyed by contacting the Investigator. Following the request from the subject, the Investigator is to provide the Sponsor with the required study and subject number so that any remaining samples and any other components from the cells can be located and destroyed. Samples will be destroyed once all protocol-defined procedures are completed. However, information collected from samples before the request for destruction, will be retained by Amgen.

The Sponsor is the exclusive owner of any data, discoveries, or derivative materials from the sample materials and is responsible for the destruction of the sample(s) at the request of the subject through the Investigator, at the end of the storage period, or as appropriate (eg, the scientific rationale for experimentation with a certain sample type no longer justifies keeping the sample). If a commercial product is developed from this research project, the Sponsor owns the commercial product. The subject has no commercial rights to such product and has no commercial rights to the data, information, discoveries, or derivative materials gained or produced from the sample. See [Appendix 5](#) for subject confidentiality.

Approved

### Appendix 3: Clinical Laboratory Evaluations

Clinical chemistry a :	Hematology a :	Urinalysis:
Alanine aminotransferase Albumin Alkaline phosphatase Aspartate aminotransferase Calcium Chloride Cholesterol Creatinine Direct bilirubin Gamma-glutamyl transferase Glucose Inorganic phosphate Potassium Sodium Total bilirubin Total protein Urea Uric acid	Hematocrit Hemoglobin Mean cell hemoglobin Mean cell hemoglobin concentration Mean cell volume Platelet count Red blood cell (RBC) count White blood cell (WBC) count WBC differential: Basophils Eosinophils Lymphocytes Monocytes Neutrophils	Blood Glucose Ketones pH Protein Specific gravity Urobilinogen Microscopic examination
Serology b :	Drug screen c :	
Hepatitis B core antibody Hepatitis B surface antigen Hepatitis B surface antibody Hepatitis C antibody Human immunodeficiency virus (HIV-1 and HIV-2) antibodies	Including, but not limited to: Amphetamines/methamphetamines Barbiturates Benzodiazepines Cocaine (metabolite) Cotinine Methadone Phencyclidine Opiates Tetrahydrocannabinol/cannabinoids Tricyclic antidepressants Alcohol breath test	
Hormone panel - females only:	Other tests:	
Follicle-stimulating hormone b (postmenopausal females only) Serum pregnancy test (human chorionic gonadotropin) d Urine pregnancy test e	Troponin I Creatine kinase-MB f	

a Blood samples for clinical chemistry and hematology.

b Only analyzed at Screening.

c Only analyzed at Screening and at Check-in of each period.

d Performed at Screening for all females.

e Performed for all females at each Check-in and the Follow-up/End of Study visit. A positive urine pregnancy test will be confirmed with a serum pregnancy test.

f CK-MB at post-baseline timepoints also to be collected if possible in the event of a suspected coronary event.

Approved

#### Appendix 4: Total Blood Volume

The following blood volumes will be withdrawn for each subject.

	Volume per blood sample (mL)	Maximum number of blood samples	Total amount of blood (mL)
Serology	3.5	1	3.5
Safety laboratory tests	7.5	7	52.5
OM pharmacokinetics	4	27	108
Moxifloxacin pharmacokinetics	2	16	32
Placebo blood sampling a	4	16	64
Troponin-I sampling	2.5	16	40
Total:			300

a Blood samples will be collected but not analyzed for the placebo treatment period.

If extra blood samples are required, the maximum blood volume to be withdrawn per subject will be less than 500 mL.

Any blood sample collected according to the Schedule of Assessments can be analyzed for any of the tests outlined in the protocol and for any tests necessary to minimize risks to study subjects. This includes testing to ensure analytical methods produce reliable and valid data throughout the course of the study. This can also include, but is not limited to, investigation of unexpected results, incurred sample reanalysis, and analyses for method transfer and comparability.

Approved

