**Study design:**

This is a single-center, single-dose (Part A; PK Evaluation Period), and randomized, 3-period, 3-treatment, crossover, single-dose (Part B) study in healthy adult subjects to determine whether OM prolongs the QTc after a single oral dose administration of 50 mg OM. Treatment in Part A will consist of a single 25-mg OM treatment (Treatment 1). Subjects whose resulting maximum observed plasma OM concentration ( $C_{max}$ ) is  $\leq 350$  ng/mL will be randomized into Part B, which consists of 3 periods wherein a single treatment is given in each period. Treatments will consist of placebo (Treatment A), OM 50 mg (Treatment B), or moxifloxacin 400 mg (Treatment C). All treatments (Part A and Part B) will be separated by a washout of at least 7 days.

Part A

All subjects will receive Treatment 1. OM treatment will be open-label. Safety and tolerability monitoring will be conducted throughout Part A, and blood samples will be collected to determine plasma OM concentrations. Safety digital ECG recordings will be reviewed by the Investigator or designee on Day -1, and on Day 1 at the following timepoints: predose and at 1, 4, 24, 48, and 120 hours postdose. Pharmacokinetic blood samples for OM will be collected at the following timepoints on Day 1: predose and 0.25, 0.5, 0.75, 1, 2, 3, 4, 6, 8, and 12 hours postdose.

Subjects whose resulting  $C_{max}$  is  $\leq 350$  ng/mL will be randomized into Part B. There will be a minimum of a 7-day washout between treatments in Part A and Part B.

Part B

After completing Part A, eligible subjects will be randomized to receive 3 treatments in 1 of 6 sequences, as follows:

Approved

Approved

Sequence	Period	Period	Period	
	1	2	3	
1	A	B	C	
2	B	C	A	
3	C	A	B	
4	A	C	B	
5	C	B	A	
6	B	A	C	

In Part B, placebo and OM treatments will be double-blinded, moxifloxacin treatment will be open-label, and the core ECG lab will be blinded to all treatment information. Safety and tolerability monitoring will be conducted throughout the study, and blood samples will be collected to determine plasma OM and moxifloxacin concentrations in relevant periods.

In each Part B treatment period, continuous digital ECG recording will be performed for approximately 27 hours, from predose through at least 24 hours postdose, and up to 10 replicate 12-lead ECGs will be extracted at the following timepoints on Day 1: -1.25, -1, and -0.75 hours predose and 0.25, 0.5, 0.75, 1, 1.5, 2, 3, 4, 8, 12, and 24 hours postdose.

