In each Part B treatment period, PK blood samples for OM and moxifloxacin will be collected at the following timepoints on Day 1: predose and 0.25, 0.5, 0.75, 1, 1.5, 2, 3, 4, 8, 12, 24, 48, 72, 96, and 120 hours postdose.

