## **7.3. Pharmacokinetic Assessments**

### **7.3.1. Pharmacokinetic Blood Sample Collection and Processing**

Blood samples for analysis of plasma OM and moxifloxacin concentrations will be obtained from all subjects in each treatment period of this study to ensure uniform study conditions. Analyses for OM will be performed on samples from subjects who receive OM and analyses for moxifloxacin may be performed (if needed) on samples from subjects who receive moxifloxacin. No analysis of blood samples taken from subjects during the placebo treatment period is planned. All other samples will be saved for analysis if needed.

Blood samples (approximately 1 × 4 mL) for OM and for moxifloxacin (approximately 1 × 2 mL) will be collected by venipuncture or cannulation at the times indicated in the Schedule of Assessments in [Appendix 6](#). Procedures for collection, processing, and shipping of PK blood samples will be detailed in a separate document.

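### Appendix 4 states 300 mL of blood per subject, but the synopsis sampling paragraph, Section 7.3.1 and the Part B schedule, taken as written, give 428 mL

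*Protocol*

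**What the plan says.** **Appendix 4 (Total Blood Volume)** presents its table as what each subject will give and totals 300 mL. Two of its rows read "OM pharmacokinetics 4 27 108" and "Moxifloxacin pharmacokinetics 2 16 32" (mL per sample, number of samples, total mL). A placebo row adds 16 samples of 4 mL, which a footnote says are collected but not analysed. Below the table stands the ceiling: "If extra blood samples are required, the maximum blood volume to be withdrawn per subject will be less than 500 mL".

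**Section 7.3.1** says that samples for OM and moxifloxacin "will be obtained from all subjects in each treatment period of this study to ensure uniform study conditions". It gives the volumes as about 4 mL for OM and about 2 mL for moxifloxacin. It then limits the assays by treatment and keeps the remaining samples in case they are needed.

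**Synopsis, Study design**, points both ways. One sentence says "blood samples will be collected to determine plasma OM and moxifloxacin concentrations in relevant periods". The sampling paragraph that follows says "In each Part B treatment period, PK blood samples for OM and moxifloxacin will be collected at the following timepoints on Day 1" and lists 16 times, from predose to 120 hours.

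**Appendix 6, Table 3 (Part B, Periods 1 to 3)** has separate rows for OM and moxifloxacin plasma PK, marked at the same 16 times. No footnote limits either row by treatment. SAP Section 4.1 repeats the 16 times without saying which tubes are drawn in which period.

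**The concern.** The Appendix 4 counts fit only one PK tube per Part B timepoint. The 27 OM samples are 11 in Part A plus 16 from a single Part B period. The 16 moxifloxacin samples come from a single period, and the placebo row has a 4-mL tube and no 2-mL tube. The sampling text and the schedule describe two tubes per timepoint in every period.

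The volume of blood taken from healthy volunteers is a burden that the protocol quantifies. A site that follows the schedule literally draws more than the stated total. A site that follows Appendix 4 omits tubes that the schedule lists. The 500-mL ceiling is written for extra samples, yet the difference here comes from scheduled ones. It uses up room that would otherwise be available for unscheduled draws, such as the serial troponin and CK-MB samples in Section 5.1.2 or the repeat liver tests in Appendix 8.

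**Working it through.** **Inputs**
- From Appendix 4: serology 3.5 mL × 1; safety laboratory 7.5 mL × 7; OM 4 mL × 27; moxifloxacin 2 mL × 16; placebo 4 mL × 16; troponin I 2.5 mL × 16.
- Part A OM times (synopsis): predose, 0.25, 0.5, 0.75, 1, 2, 3, 4, 6, 8 and 12 h, so 11.
- Part B PK times per period (synopsis, SAP Section 4.1): predose, 0.25, 0.5, 0.75, 1, 1.5, 2, 3, 4, 8, 12, 24, 48, 72, 96 and 120 h, so 16.
- Tube volumes (Section 7.3.1): 4 mL for OM, 2 mL for moxifloxacin.

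**Step 1. Reproduce the plan's total**

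3.5 + 52.5 + 108 + 32 + 64 + 40 = 300 mL. The table adds up. Its OM count is 11 + 16 = 27.

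**Step 2. Part B PK blood under each description**
- Appendix 4, one tube by treatment: 16 × 4 + 16 × 2 + 16 × 4 = 64 + 32 + 64 = 160 mL.
- Synopsis sampling paragraph and schedule, both tubes in every period: 3 × 16 × (4 + 2) = 288 mL.
- Difference: 288 − 160 = 128 mL.

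**Step 3. Total with both tubes in every period**
- OM: 4 × (11 + 3 × 16) = 4 × 59 = 236 mL.
- Moxifloxacin: 2 × (3 × 16) = 2 × 48 = 96 mL.
- Serology, safety laboratory and troponin, as tabulated: 3.5 + 52.5 + 40 = 96 mL.
- Total: 236 + 96 + 96 = 428 mL.
- Excess over the stated total: 428 − 300 = 128 mL, and 128 / 300 = 43%.

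**Step 4. Room under the ceiling**
- As Appendix 4 implies: 500 − 300 = 200 mL.
- With both tubes: 500 − 428 = 72 mL.

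**Step 5. Sensitivity to the other counts**
- The Part A schedule row, as extracted, seems to show 12 OM marks where the text lists 11 times. The table is broken in extraction. Twelve would give 428 + 4 = 432 mL.
- The schedule rows appear to allow up to 21 troponin samples against the 16 tabulated. If each were a separate 2.5-mL draw, the total would be 428 + 5 × 2.5 = 440.5 mL. This is a separate question and depends on whether some troponin shares a safety-laboratory tube.
- Both changes together give 428 + 4 + 12.5 = 444.5 mL. All variants are below 500 mL.

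**The case against.** The strongest reply is that Appendix 4 may be a deliberate count. Section 7.3.1 does not say in terms that both tubes are drawn in each period. It can be read as one PK draw per timepoint in every period, placebo included, with the tube set by treatment. The synopsis phrase about relevant periods agrees. The pattern also suits the blinding in Section 5.5: draws are equal in the double-blind OM and placebo periods and differ only in the open-label moxifloxacin period. Subjects would still be bled at the same 16 times in all three periods, so uniform conditions are not clearly lost. Section 7.3.1 also leaves collection procedures to a separate document that is not available here.

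Much of this stands. Section 7.3.1 alone is ambiguous, and which text governs cannot be settled from the documents. But the one-tube reading does not fit the synopsis paragraph that names both analytes in each Part B period. Nor does it fit the schedule. The schedule's treatment row covers the three periods by listing the treatments as alternatives, whereas the PK rows are separate and unqualified. Elsewhere the same table uses footnotes to restrict sampling, to end of study or to Period 1.

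Two further objections also stand. The documents do not show that 72 mL is too little. They give no volumes for serial CK-MB or repeat liver tests, and 72 mL would cover 28 draws at the tabulated 2.5 mL. And none of this touches the primary endpoint, the analysis sets, the power or the decision rule.

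**Conclusion.** The protocol is internally inconsistent and needs correcting. Either the stated per-subject total or the sampling text and schedule is wrong as written. The two descriptions give 300 mL and 428 mL, a difference of 128 mL (43%). The 428 mL assumes a 4-mL and a 2-mL tube at all 16 times in each of three periods, 11 OM samples and no moxifloxacin tube in Part A, and the other Appendix 4 rows unchanged. The arithmetic is certain. Confidence about which text is operative is only moderate.

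A reader might infer more than the documents support:
- **That the table is mis-added.** It is not. The rows sum to 300 mL, and the conflict is over which tubes are counted.
- **That the ceiling is broken.** It is not. Both totals, and every variant above, are below 500 mL, and the ceiling sentence is not itself wrong under either reading.
- **That Amendment 3 set out to correct this table and missed the PK rows.** Its summary of changes limits the purpose to troponin volume and sample count, so leaving the PK rows alone was within its scope.
- **That moxifloxacin tubes are also due in Part A.** Section 7.3.1 could be stretched that far, which would add 11 × 2 = 22 mL and give 450 mL, but the Part A schedule lists only OM sampling.

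**What to change.** Make both statements in the synopsis Study design section, Section 7.3.1, the Part B schedule in Appendix 6 and the Appendix 4 table name the same tubes in each period, then restate the Appendix 4 total to match. If both tubes are drawn in every period, the total becomes 428 mL and the phrase about relevant periods needs rewording. If one tube per period is intended, 300 mL can stand, but the synopsis sampling paragraph, Section 7.3.1 and the two schedule rows must say so, for example with a footnote by treatment. The sponsor must choose; the documents do not settle it.

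The separate sample-collection document, and any participant information that repeats the volume, should be checked against the result. Neither was available here. The cost is protocol wording and one corrected table. If both tubes stay, the stated burden on volunteers becomes less favourable. No analysis changes.
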